### 5.2 Safety Evaluations

After participants are enrolled at 3-4 weeks during the treatment period, a study coordinator will contact each participant to check compliance, tolerability, and side effects with ALA supplementation. Any concern for a potential adverse event will be reviewed by the study investigators. In addition, tolerability and side effects will be reviewed at each scheduled, four-month clinic visit. All adverse events will be reviewed by the study investigators. Depending on the severity of the adverse event, the study investigator may determine the need for un-blinding, and the participant may be advised to stop ALA intake if it is determined that ALA is the cause.

In addition, during the informed consent process, all potential side effects and drug interactions will be discussed. Enrolled participants will be provided the email address of the study coordinator and a 24-hour contact phone number of a physician if any adverse events occur during the study period.

When 50% of participants have been in the study for 6 months, an interim analysis will be performed. If it is found that clinical outcomes for ALA-treated participants are significantly improved compared to the placebo arm, study investigators may elect to complete the trial early and provide all participants with ALA.

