### 8.2 Blinding

Both participants and study team members will be blinded to treatment arm. The following study procedures will be in place to ensure double-blind administration of study treatments:

- Randomization will occur at time of first screening visit and results will be

provided to the UCSF Pharmacy compounding services

- Randomization will be controlled by the UCSF Pharmacy compounding service who will provide treatment packages to the study coordinator who will provide them to the study participant. Treatment packages will contain insert materials but no markings that will allow participants to know which study arm they have been randomized to.
- Access to randomized code will be strictly controlled; study investigators and clinical coordinators will not have access to the randomized code unless a need for un-blinding arises.
- Packaging and labeling of test and control treatments will be identical.

The study blind will be broken on completion of the clinical study and after the study database has been locked. In the event of an adverse event, the study investigator may decide to un-blind himself to determine if ALA is the cause. In addition, when 50% of target participants have been enrolled and on the study protocol for 6 months, an interim analysis will be performed by an un-blinded statistician to evaluate for ALA clinical effects. At that point, if it is found that clinical outcomes for ALA-treated participants are significantly improved compared to the placebo arm, study investigators may elect to complete the trial early and provide all participants with ALA.

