### **9.1.7 Adverse Events**

Information regarding occurrence of adverse events will be captured throughout the study. Duration (start and stop dates and times), severity/grade, outcome, treatment and relation to study drug will be recorded on the case report form (CRF).

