## 11 ADVERSE EXPERIENCE REPORTING AND DOCUMENTATION

### 11.1 Adverse Events

An adverse event (AE) is any untoward medical occurrence in a clinical investigation of a participant administered a pharmaceutical product and that does not necessarily have a causal relationship with the treatment. An AE is therefore any unfavorable and unintended sign (including an abnormal laboratory finding), symptom or disease temporally associated with the administration of an investigational product, whether or not related to that investigational product. An unexpected AE is one of a type not identified in nature, severity, or frequency in the current Investigator's Brochure or of greater severity or frequency than expected based on the information in the Investigator's Brochure.

The Investigator will probe, via discussion with the participant, for the occurrence of AEs during each participant visit and record the information in the site's source documents. Adverse events will be recorded in the participant CRF. Adverse events will be described by duration (start and stop dates and times), severity, outcome, treatment and relation to study drug, or if unrelated, the cause.

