**Table 2. AE Relationship to Study Drug**

Relationship to Drug	Comment
Definitely	Previously known toxicity of agent; or an event that follows a reasonable temporal sequence from administration of the drug; that follows a known or expected response pattern to the suspected drug; that is confirmed by stopping or reducing the dosage of the drug; and that is not explained by any other reasonable hypothesis.
Probably	An event that follows a reasonable temporal sequence from administration of the drug; that follows a known or expected response pattern to the suspected drug; that is confirmed by stopping or reducing the dosage of the drug; and that is unlikely to be explained by the known characteristics of the participant's clinical state or by other interventions.
Possibly	An event that follows a reasonable temporal sequence from administration of the drug; that follows a known or expected response pattern to that suspected drug; but that could readily have been produced by a number of other factors.
Unrelated	An event that can be determined with certainty to have no relationship to the study drug.

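### The investigator may open the code to judge whether ALA caused an adverse event, and nothing available requires relatedness to be recorded first, so relatedness ratings are biased against ALA in proportion to the share un-blinded before scoring

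*Combined protocol and SAP*

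**What the plan says.** Four parts of the protocol bear on this point.

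- **When the code may be opened.** Section 8.2 (Blinding) keeps the code closed in general: "study investigators and clinical coordinators will not have access to the randomized code unless a need for un-blinding arises". It then gives a ground for opening it: "In the event of an adverse event, the study investigator may decide to un-blind himself to determine if ALA is the cause". Section 5.2 (Safety Evaluations) gives a different condition: "Depending on the severity of the adverse event, the study investigator may determine the need for un-blinding". The synopsis entry on safety evaluations repeats the 5.2 rule.
- **What follows from the judgement.** Section 5.2 adds that "the participant may be advised to stop ALA intake if it is determined that ALA is the cause".
- **Who assesses events and what is recorded.** Section 5.2 states: "All adverse events will be reviewed by the study investigators". Section 11.1 states: "Adverse events will be described by duration (start and stop dates and times), severity, outcome, treatment and relation to study drug". Section 9.1.7 places the same items on the CRF. Neither section says whether the rating is made before or after a code break.
- **How relatedness is graded.** Table 2 in section 11.1 has four levels: Definitely, Probably, Possibly and Unrelated. The lowest is defined as "An event that can be determined with certainty to have no relationship to the study drug". Possibly covers an event with suitable timing and response pattern that other factors could also explain.

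Section 15 describes no safety analysis. It defers detail to an SAP to be written before the final data are analysed. Section 11.3 and the study manual mentioned in section 11.1 were not available for review.

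**The concern.** A blinded placebo arm shows how often events would be called drug-related when no drug was given. That works only if the rater does not know the arm. Section 8.2 makes causality itself the reason for learning the arm, and the people who may open the code are the people who review the events.

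The resulting error runs in one direction. Knowing that a participant took sucrose settles that ALA was not the cause. Knowing that a participant took ALA settles nothing, and the event can still be rated Possibly or higher. Any later table of related events, or of stops made because ALA was judged the cause, would lean against ALA.

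This matters although no such table is yet planned. Section 4.1 gives adverse events resulting from ALA as one reason for the two-year follow-up. The longest ALA exposure cited in section 2.1 is 600 mg daily for 4 years, while this trial gives 1200 mg daily for 3 years, so its safety record will be read as new information. A rating made with knowledge of the arm cannot be re-made blind by the same person.

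**Working it through.** The plan states no figure on this point, so there is none to reproduce. The check first compares the sections, then sizes the bias under stated assumptions.

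**1. The sections side by side**

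| Question | Section 8.2 | Section 5.2 and synopsis |
|---|---|---|
| Which events? | An adverse event, with no severity condition | Depends on severity |
| Stated purpose | To find out whether ALA is the cause | None in that clause; advice to stop follows if ALA is found to be the cause |
| Obligatory? | No, at the investigator's discretion | No, at the investigator's discretion |
| Relatedness recorded first? | Not stated | Not stated |

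**2. The mechanism**

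Table 2 refers to the study drug and section 8.2 to ALA; they are read here as the same thing. For a placebo participant whose code has been opened, ALA is excluded with certainty, which is Table 2's condition for Unrelated. For an ALA participant, opening the code rules out no category.

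**3. Inputs for the size**

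- n = 25 per arm (section 4.1).
- q = share of participants with an event that a blinded assessor would call related. Assumed, not in the documents: 0.20 to 0.50, equal in both arms, so the true difference is zero.
- u = share of those events un-blinded before scoring. Assumed, not in the documents: 0 to 1.
- Ratings on ALA are assumed unchanged by un-blinding.

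**4. Formulas**

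- Expected related share on ALA = q.
- Expected related share on placebo = q × (1 − u).
- Spurious difference = q − q(1 − u) = q × u.
- False rejection = probability that a two-sided Fisher exact test at 0.05 rejects, summed over all pairs of binomial counts with n = 25.

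**5. Results**

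At q = 0.30 the expected shares, ALA against placebo, are:

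- u = 0.25: 30% against 0.30 × 0.75 = 22.5%
- u = 0.50: 30% against 0.30 × 0.50 = 15%
- u = 0.75: 30% against 0.30 × 0.25 = 7.5%
- u = 1: 30% against 0%

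False rejection:

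| q | u = 0 | u = 0.25 | u = 0.50 | u = 0.75 | u = 1 |
|---|---|---|---|---|---|
| 0.20 | 2.2% | 3.5% | 8.6% | 19.8% | 38.3% |
| 0.30 | 2.3% | 4.6% | 15.0% | 41.7% | 80.7% |
| 0.40 | 3.0% | 7.0% | 23.1% | 59.1% | 97.1% |
| 0.50 | 3.3% | 10.5% | 35.8% | 75.7% | 99.8% |

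The u = 0 column is the position if relatedness is always scored first. The expected difference is zero and rejection stays below the nominal 5%.

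**6. Hand check of the last column**

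With u = 1 the placebo count is always 0, and the two-sided Fisher p for k against 0 is 2 × C(25,k)/C(50,k).

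- k = 5: 2 × 53,130/2,118,760 = 0.0502, not significant.
- k = 6: 2 × 177,100/15,890,700 = 0.022.
- k = 7: 2 × 480,700/99,884,400 = 0.0096.

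The test therefore rejects when ALA has 6 or more. At q = 0.30 that probability is 1 − 0.1935 = 0.8065, which agrees with the table.

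**The case against.** The case on the other side is substantial, and much of it stands.

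- **Un-blinding is optional.** A reader might infer that placebo events in general become Unrelated. The documents do not support that. Both sections leave the decision to the investigator, section 5.2 and the synopsis make it depend on severity, and section 8.2 otherwise restricts access to the code. Only placebo events un-blinded before scoring are affected.
- **No related-event comparison is planned.** A reader might infer that the trial's safety comparison has lost its control. Section 15 contains no such comparison. Section 11.1 defines adverse events without regard to relatedness, so a comparison of all events remains available and is not filtered in this way.
- **Discontinuation.** A reader might infer that stopping for an adverse event can occur only on ALA. Section 12.1 lets a participant in either arm stop for an adverse event without any causality finding. Only stops made because ALA was judged the cause are specific to one arm.
- **The extreme table.** A result of 7/25 against 0/25 (p = 0.0096) is striking, but it needs every such placebo event to be un-blinded first. At one quarter un-blinded and q = 0.30, false rejection is 4.6%, still under the nominal level.
- **How many could trigger it.** From the sample-size rates and an assumed Poisson count, 1 − e^(−3) = 95% of placebo and 1 − e^(−1.5) = 78% of ALA participants would have a stone event in 3 years: 25 × 0.950 + 25 × 0.777 = 43.2 of 50. A reader might take that as the reach of the un-blinding rule. It counts stone events, not code breaks. Moreover, the ALA side effects described in section 2.1 are mainly minor gastrointestinal ones, and Table 2's Possibly requires a response pattern known or expected for the drug.
- **Unseen material.** Section 11.3 or the study manual may contain a relevant rule.

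These points limit the reach of the concern but do not remove it. Section 8.2 names causality as a reason to open the code, and no available section sets the order of rating and code break.

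**Conclusion.** The concern holds in a limited form. The un-blinding rules in section 8.2 and in section 5.2 with the synopsis differ and are not reconciled. Placebo events un-blinded before scoring become Unrelated by construction, and ALA events do not. The spurious difference in related events is q × u.

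The documents supply neither quantity, so the false-rejection figures illustrate the mechanism and do not forecast the trial. They rest on equal true event shares, one rating per participant, and ALA ratings unaffected by un-blinding. Under those assumptions the effect is negligible when few events are un-blinded. At q = 0.30 it reaches three times the nominal 5% when half are un-blinded (15.0%).

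Severity is moderate. Un-blinding is discretionary, no planned analysis depends on relatedness, and all-event counts are unaffected. The repair is a cheap improvement, and it must be in place before ratings are made.

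**What to change.** 1. In sections 8.2 and 5.2, and in the matching synopsis entry, require severity and relationship to be entered and signed in the CRF before any code break, and not changed afterwards.
2. Have the pharmacy release only the assignment of the participant concerned, and log the time and reason for each release.
3. Specify in section 15 and the SAP that the main safety table compares all adverse events by arm, regardless of relatedness. If related events are also tabulated, use the signed rating and report the number of code breaks by arm.
4. Reconcile sections 8.2, 5.2 and the synopsis on when un-blinding is allowed, and on how the advice to stop relates to the blind. No un-blinding criterion, stopping rule or other clinical rule is proposed here.
5. Check section 11.3 and the study manual for any rule that already covers items 1 or 2.

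The cost is protocol wording, one CRF field (the time of the relatedness entry, to set against the time of any code break) and a short step before a code is opened. No added staff are needed.

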PRIMARY ENDPOINT	
The primary efficacy endpoint will be assessed in two ways over the course of the 3-year treatment period:
 
 
1) symptomatic stone recurrences, defined as renal colic, stone passage, or surgical removal of a stone;
 
2) silent stone recurrences, classified as stone growth or new stones,
 

	diagnosed on the basis of renal ultrasound, plain KUB x-ray, or if clinically indicated, computed tomography.
SAFETY EVALUATIONS	After participants are enrolled at 3-4 weeks during the treatment period, a study coordinator will contact each participant to check compliance, tolerability, and side effects with ALA supplementation. Any concern for a potential adverse event will be reviewed by the study investigators. Patient clinical care will continue as per the current standard for the duration of this study. Tolerability and side effects will be reviewed at each scheduled clinic visit which normally occur every four months. All reported adverse events will be reviewed by the study investigators. Depending on the severity of the adverse event, the study investigator may determine the need for un-blinding, and the participant may be advised to stop ALA intake if it is determined that ALA is the cause.
PLANNED INTERIM ANALYSES	When 50% of target participants have been enrolled and on the study protocol for 6 months, an interim analysis will be performed by an un-blinded statistician to evaluate for ALA clinical effects.
STATISTICS Primary Analysis Plan	The analysis will be performed on the intention-to-treat principle in the treatment and placebo groups. The primary efficacy endpoint will be assessed by comparing the rates of symptomatic and silent stone recurrences using the t-test with a two-sided p-values and calculated 95% confidence intervals. In addition, the analysis of secondary endpoints will compare quantitative urinary cystine, and metallomic and metabolomics profiles using repeated measures of analysis of variance.

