Rationale for Number of Participants	The target enrollment for this study is 50 participants, based on a conservative approach to determine the sample size needed to evaluate the effect of ALA supplementation. Two recent studies evaluating the medical management of cystinuric individuals have reported that among individuals who are compliant in taking medications, the average number of stone events per person is approximately 1 per year (Reference #'s 5, 9). The current study design will be powered at 90% to detect a clinically meaningful reduction of stone events at 50% (0.5 stone events per year) with two-tailed $\alpha = 0.05$ . Based on a two-sided t-test, the following scenarios were considered for the standard deviation (SD) for the sample and sample size (n): SD 0.5, n=11; SD 0.75, n=24; SD 1, n=42. To account for a small dropout rate over the study duration, the enrollment goal of 50 participants was proposed.

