Clinical data including medical history, plain KUB x-ray and renal ultrasound, routine blood work, and 24-hour urine collections for all participants will be collected as part of normal clinical care at routine clinical visit intervals, which currently occur every 4 months. Routine clinical care for participants will not be altered in any way outside of administration of the supplement or placebo. Routine clinical care generally consists of office visits every 4 months at which time, as medically necessary as determined by the study investigator, an imaging study is performed (plain KUB x-ray, ultrasound, or CT scan if clinically indicated), a 24-hour urine collection is done to check quantitative urinary cystine levels, and blood is drawn to evaluate electrolyte levels as well as renal function. During routine visits for blood and urine tests, any discarded blood and urine specimens will be collected for research testing. No additional blood draw or urine collection will be performed for this study. From discarded routine specimens provided during these clinic visits, metallomic and metabolomics profiling will be performed for all participants using discarded samples material. This is comprised of mass spectrometry and elemental analysis of samples performed in our research lab. Quality of life measurement, as recorded by the Wisconsin Stone-quality of life questionnaire (Wisconsin Stone-QoL), will also be evaluated.

Recurrent stone events, defined by symptomatic or silent stone recurrence, is the primary endpoint in this study. It will be documented in this study cohort, and compared between treatment and placebo groups to determine treatment effect. If stones are removed for surgery or spontaneously passed by participants, any discarded stone specimens not needed for clinical care will also be subjected to metabolomic and metallomic analysis.

At the end of the three years of study drug treatment, all participants will undergo a low dose non-contrast CT scan to look for a silent change in stone size. As this is a pilot study, recruitment will be limited to target enrollment of 50 participants (25 for each treatment arm). Treatment will continue for a total of 3 years and after treatment completion, participants will be followed for an additional 2 years to evaluate for change in clinical status or adverse events resultant from ALA administration.

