### 15.3 Sample Size and Randomization

The target enrollment for this study is 50 participants, based on a conservative approach to determine the sample size needed to evaluate the effect of ALA supplementation. Two recent studies evaluating the medical management of cystinuric individuals have reported that among individuals who are compliant in taking medications, the average number of stone events per person is approximately 1 per year (Reference #'s 5, 9). The current study design will be powered at 90% to detect a clinically meaningful reduction of stone events at 50% (0.5 stone events per year) with two-tailed  $\alpha = 0.05$ . Based on a two-sided t- test, the following scenarios were considered for the standard deviation (SD) for the sample and sample size (n): SD 0.5, n=11; SD 0.75, n=24; SD 1, n=42. To account for a small dropout rate over the study duration, the enrollment of 50 participants was proposed. At UCSF, clinical volume approximates 60 nephrolithiasis patients per week, including those with cystinuria. At a recent cystinuria outreach event led by [name] at UCSF (<http://[name].ucsf.edu/?q=news/june-18-2015-cystine-patient-symposium>), over 50 individuals with cystinuria attended among over 100 participants overall. We anticipate that 6-8 months will be required to accrue these participants.

Participants will be computer sequence-randomized to receive either ALA or placebo.

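### The interim look permits a stop for benefit with no boundary or alpha adjustment; at the only significance level stated, the false-benefit probability rises from 2.5% to about 4.4–4.8%

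*Combined protocol and SAP*

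**What the plan says.** The synopsis gives the task to an un-blinded statistician and sets the timing: "When 50% of target participants have been enrolled and on the study protocol for 6 months, an interim analysis will be performed". Section 5.2 has the same look: "When 50% of participants have been in the study for 6 months, an interim analysis will be performed". Sections 5.2 and 8.2 attach the same consequence. If "clinical outcomes for ALA-treated participants are significantly improved compared to the placebo arm, study investigators may elect to complete the trial early", every participant then receives ALA.

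The other relevant provisions are these:

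- **Significance level.** The only alpha is two-tailed 0.05, in the sample-size text (synopsis and Section 15.3). The synopsis specifies a two-sided t-test with 95% confidence intervals for the primary comparison.
- **Section 15.** The table of contents lists a Section 15.5 on interim analysis. The body runs only from 15.1 to 15.3 and does not mention the interim.
- **SAP timing.** Section 15 requires a detailed SAP before the final data are analysed. Nothing requires it before the interim.
- **Blinding.** Section 8.2 keeps participants and study team blinded. It does not say what the statistician passes on. Section 14, on data safety monitoring, deals with privacy and data security and provides for no independent interim review.
- **Endpoint timing.** The primary endpoint covers the 3-year treatment period. The one CT required of everyone is at month 36 (Sections 9.1.6, 10 and 10.3; Appendix 1).

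**The concern.** This is an operative stopping rule, not just a missing detail. Applied as written, it gives the trial two chances to declare benefit, the first on a small share of the planned follow-up, with nothing set aside to pay for it. Three things are at stake:

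- **Error rate.** The final p-value and 95% interval would not have their nominal properties.
- **Size of the reported effect.** A result that crosses 0.05 on few events tends to be an overestimate, and a stop would make it the trial's result.
- **Silent recurrence.** At the look nobody is near month 36. Giving everyone ALA would end the randomised comparison before the systematic CT.

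The interim endpoint is described only as clinical outcomes. The primary endpoint is itself assessed in two ways, so the choice of outcome is open as well.

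**Working it through.** **The plan's own figures.** No interim level, boundary or information fraction is given, so there is none to reproduce. The only design calculation is the sample size: "SD 0.5, n=11; SD 0.75, n=24; SD 1, n=42". With power 90%, two-sided 0.05 and a difference of 0.5, (SD × (1.960 + 1.282)/0.5)² gives 10.5, 23.6 and 42.0. A two-sample t-test needs twice that in each arm: 22, 48 and 85. The stated numbers therefore do not reproduce as a two-arm calculation. That is a separate matter, and nothing below depends on it.

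**Step 1: how much follow-up is in hand.** Inputs are 50 participants, 25 per arm, 3 years of treatment (50 × 3 = 150 person-years) and accrual over 6–8 months (Sections 4.1 and 15.3). Uniform accrual is my assumption.

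| | 6-month accrual | 8-month accrual |
|---|---|---|
| Month of the look (25th entry + 6) | 3 + 6 = 9 | 4 + 6 = 10 |
| First 25 only | 25 × 7.5/12 = 15.6 py (10.4%) | 25 × 8/12 = 16.7 py (11.1%) |
| All 50 | 50 × 6/12 = 25 py (16.7%) | 50 × 6/12 = 25 py (16.7%) |

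If each of the 25 contributes exactly six months, the figure is 12.5/150 = 8.3%.

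These are person-time fractions. Statistical information is larger when participants differ in their underlying rates. Take a rate of 1 per year ("the average number of stone events per person is approximately 1 per year") and the plan's SD of 1 for a 3-year average. The between-person variance is then 1 − 1/3 = 0.667. For the first 25 with 7.5 months each, the fraction is 0.5 × 1/(1/0.625 + 0.667) = 0.22. Simulations using all 50, with their unequal follow-up, give 0.33–0.35.

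**Step 2: type I error.** Assume nominal two-sided 0.05 at both looks and a stop for benefit only. With information fraction t, the two test statistics are approximately bivariate normal with correlation √t. Then P(false benefit) = 0.025 + 0.025 − P(both exceed 1.96). A two-sided final test adds about 0.025 for a false harm finding.

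| t | P(both) | False benefit | Total with final harm |
|---|---|---|---|
| 0.083 | 0.0023 | 0.0477 | 0.073 |
| 0.111 | 0.0027 | 0.0473 | 0.072 |
| 0.167 | 0.0035 | 0.0465 | 0.072 |
| 0.35 | 0.0061 | 0.0439 | 0.069 |

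The inflation is 0.0439/0.025 = 1.76 to 0.0477/0.025 = 1.91. Simulated t-tests on event counts give 0.042–0.048 for false benefit, so the result does not depend on the normal approximation or on the exact fraction.

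**Step 3: what a crossing would show if the planned effect is true.** These are simulated t-tests at 1.0 versus 0.5 events per year, with 6-month accrual.

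| Data used | Variation | P(cross for benefit) | Mean reduction when crossed |
|---|---|---|---|
| First 25 | Poisson only | 18% | 1.09/year |
| First 25 | SD 1 | 13% | 1.21/year |
| All 50 | Poisson only | 27% | 0.92/year |
| All 50 | SD 1 | 22% | 1.01/year |

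Across the accrual and variance scenarios examined, the ranges are about 12–29% and 0.9–1.25 events per year, against a truth of 0.5.

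**Step 4: a boundary of two-sided p<0.001 at the look (Haybittle–Peto).** With the final test at 0.05, overall two-sided error is 0.0507–0.0508 for t = 0.083–0.167. A final level of about 0.049 brings it to 0.05.

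**The case against.** The strongest defence is that the stop is discretionary, the study calls itself a pilot, and the later SAP may modify the plan and could add a boundary. The documents also never say that 0.05 applies at the interim. The last point stands as a condition: the figures in Step 2 assume nominal 0.05 at both looks and action whenever it is crossed. The rest does not rescue the rule. The trial is sized for 90% power at a stated two-sided alpha, and nothing requires the SAP to exist before the look.

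A reader might infer more than the documents support:

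- **That an early stop loses all silent-recurrence data.** Silent recurrence is also defined by ultrasound and KUB, which Sections 10 and 10.2 provide for at earlier visits when medically necessary. What goes is the systematic randomised CT comparison, and only if the trial stops.
- **That significance at the look needs a reduction of at least 0.88–1.01 events per year (0.70 with all 50).** Those values fix the standard error at the planned rates. A t-test uses the sample variance, and in simulation about 13–25% of significant interim results fell below them.
- **That only a grossly exaggerated effect could cross.** This holds for a true effect near 0.5 per year. A near-complete effect, as in the mouse data of Section 2, would cross without gross exaggeration.
- **That overall error is 9.3–9.5%.** That needs a stop for harm at the interim, which the rule does not contain.
- **That investigators will see arm results.** Section 8.2 leaves this open. The defect is that no firewall is specified.

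**Conclusion.** The concern holds. The plan permits an efficacy stop at about 10–17% of planned person-time (up to about 35% of statistical information if between-person variation is large), with no boundary, endpoint, alpha adjustment or reporting limit. At nominal two-sided 0.05 on both looks, the chance of a false benefit claim is about 4.4–4.8% instead of 2.5%, and total error is about 7%. If the planned effect is true, a crossing is uncommon and overstates it about twofold on average. These sizes rest on uniform accrual over 6–8 months and on reading significance as the only level the plan states. The inflation stays at about 1.7–1.9-fold over the whole range of fractions considered. The plan should be corrected before the look, because neither the error rate nor a breach of blinding can be repaired afterwards.

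**What to change.** In the synopsis, Sections 5.2 and 8.2, and a new interim subsection of Section 15:

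1. Replace the reference to significant improvement with a boundary of two-sided p<0.001 for the primary stone-event comparison, naming the event count to be tested.
2. State the final level: 0.05 (overall about 5.1%), or about 0.049 if exactly 5% is wanted.
3. Require these terms to be in the SAP before the interim analysis.
4. Have the un-blinded statistician tell the investigators only to continue or that the boundary is crossed, with no arm-level results unless it is crossed.

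Dropping the efficacy look altogether is open to the sponsor but not required. The cost is protocol and SAP wording, with no change in sample size, visits or data collection. The downside is that an early stop for benefit becomes unlikely.
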